7.5 DATA COLLECTION AND DATABASE MANAGEMENT

The study will leverage an Electronic Data Capture (EDC) for data collection. Designated full trained site staff will be responsible for handling and entry of all patient-level data into the eCRF as outlined in the protocol. Each eCRF have been built using fully validated secure web-enabled software that conforms to 21 CFR Part 11 requirements. The investigator is responsible for assuring that the data entered into the eCRF is complete, accurate and that the entry and updates are performed in a timely manner.

The EDC system in place will run automatic validation program checks to identify any data discrepancies in the eCRFs for efficient query resolution. In the event that a query is flagged, the system allows for modification and or verification of the entered data by designated staff if needed. Electronic data queries stating the nature of the problem and requesting clarification will be created for discrepancies and missing values and sent to the investigational site via the EDC system for prompt review and resolution by site staff.

After final database lock, the investigator will receive copies of the participant data for archiving at the investigational site.

Sponsor Name: Woebot Health

Protocol Number: WB001-001

All data should be recorded, handled, and stored in a way that allows its accurate reporting, interpretation, and verification.

Additional security measures, data validation steps etc. during and post database lock will be outlined in a Data Management Plan (DMP) which will describe how to handle the data under foreseeable circumstances (e.g., how data will be recorded, tracked, verified for quality control, transferred, and extracted according to FDA guidelines). Along with the DMP, a Data Validation Plan (DVP) containing all edit-checks to be performed and the calculations for derived variables are also prepared.

7.6 QUALITY CONTROL AND QUALITY ASSURANCE

The Sponsor maintains a robust Quality Management System (QMS) that includes all activities involved in quality assurance and quality control per 21 CFR 820, to ensure compliance with written SOPs as well as applicable global/local GCP regulations and ICH Guidelines.

Audits of investigator sites, vendors, and Sponsor systems are performed by auditors, independent from those involved in conducting, monitoring, or performing quality control of the clinical trial. The clinical audit process uses a knowledge/risk-based approach.

Audits are conducted to assess 21 CFR 820 and GCP compliance with global and local regulatory requirements, protocols and internal SOPs and are performed according to specified Sponsor processes.

8. STATISTICAL ANALYSIS

8.1 GENERAL METHODOLOGY

Analyses will be performed using SAS® (SAS Institute, Cary, NC, US) and R (R Core Team (2021). R Foundation for Statistical Computing, Vienna, Austria. <https://www.R-project.org/>). Each analysis will be conducted by a blinded statistician, and the statisticians will not confer until QC. The DSMB statistician will be unblinded and generate the randomization schedule. The interim re-estimation of sample size will be conducted by blinded pair programming, as with the main analysis. All personnel involved with the analysis of the study will remain blinded until database lock and identification of protocol deviations, unless otherwise mentioned in the protocol (e.g., DSMB statistician performing randomization and analysis requested by DSMB members).

The statistical analysis plan (SAP) will be approved prior to the interim analysis performed by the blinded independent statistician, and otherwise prior to any lock of the study database and unblinding of the study data. The SAP will provide a detailed description of the statistical methods and expand on the details provided in the protocol.

All data will be presented by treatment group. Descriptive statistics (number of observations, mean, standard deviation [SD], median, interquartile range [q25 and q75], and range [minimum and maximum]) will be provided for continuous variables, and counts and percentages will be presented for categorical variables.

Baseline is defined as the last non-missing measurement before or on the date of first use of the investigational device.

Sponsor Name: Woebot Health

Protocol Number: WB001-001

All statistical tests will be 2-sided and performed at the 0.05 level of significance unless stated otherwise. Descriptive analyses and p-values will be presented for exploratory endpoints.

Checks of assumptions (e.g., normality) underlying statistical procedures will be performed and appropriate corrective procedures will be applied (e.g., transformation or nonparametric tests) prior to statistical testing.

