- Must have current mild-moderate depression as measured by the HAM-D6 score > 7 and < 13 (i.e., between 8-12, inclusive) at screening (Bech et al., 2007; Pridmore et al., 2020)
- Participant must confirm having a form of TAU, defined as clinician supervised outpatient care management and includes follow-up visits, medication, psychotherapy, or some combination thereof
- As part of TAU during the study, any confirmed concomitant medications and/or psychotherapy are permissible and must be regularly scheduled or stable (dose and frequency) for over 4 weeks prior to baseline (BL) visit

Key Exclusion Criteria:

- Gestation less than 28 weeks
- HAM-D6 score ≤ 7 or ≥ 13 (severe depression) at Screening
- Currently pregnant or plans to become pregnant within the next 8 weeks
- History of drug and/or alcohol use disorder within the past 12 months measured by the SCID-5-CT (Williams JB, 2015)
- Lifetime history of suicide attempt or ideation with a plan and intent to harm oneself during the current episode of PPD
- Current or lifetime psychosis, including history of post- and peri-partum psychosis as measured by the SCID-5-CT (Williams JB, 2015)
- Current or lifetime history of schizophrenia, schizoaffective disorder, bipolar disorder, and/or homicidal or infanticidal ideation as measured by the SCID-5-CT (Williams JB, 2015)
- History of antidepressant treatment with ketamine/esketamine, electroconvulsive therapy, vagal nerve stimulation, or a deep brain stimulation device
- Fetal demise within the past 18 months
- Previous Woebot use

Study Conditions: 1:1 randomization to either [WB001+TAU] or [ED001+TAU]

Control Device: The educational control application is an educational app named ED001.

Sponsor Name: Woebot Health

Protocol Number: WB001-001

Treatment as Usual (TAU): Participants will receive TAU, which is clinician supervised outpatient care including follow-up visit(s), psychotropic medication, psychotherapy, or some combination thereof.

Primary Endpoint: Difference in HAM-D6 scores between groups at EOT, controlling for baseline (BL) and other covariates

Secondary Endpoints:

1. Difference between arms in the following assessments at EOT, controlling for BL and other covariates:

- Edinburgh Postnatal Depression Scale (EPDS)
- Maternal-Infant Bonding Scale (MIBS)
- Patient Health Questionnaire-9 (PHQ-9)
- Generalized Anxiety Disorder-7 (GAD-7)

2. Difference in HAM-D6 scores within arms between BL and EOT

Exploratory Endpoints:

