- Change from baseline in Clinical Global Impression-Improvement (CGI-I) the CGI-Severity (CGI-S) at Week 4 and Week 8
- Change from baseline in Patient Global Impression-Change (PGI-C) and Patient Global Impression-Severity (PGI-S) at Week 4 and Week 8
- Client Satisfaction Questionnaire-8 at Week 8

Safety Endpoints: C-SSRS and Adverse Events (AEs), Serious Adverse Events (SAEs)

Safety Aim: To evaluate the safety of [WB001+TAU] versus [ED001+TAU] based on PI and Sponsor determined AE and SAEs. The study will use the Columbia-Suicide Severity Rating Scale (C-SSRS), the PHQ-9 item #9, and the EPDS item #10, and the HAM-D17 item #3 to facilitate identification of AEs and SAEs. It would be separately determined whether identified AEs or SAEs are related to the device.

Statistical Methods: The primary efficacy endpoint is the difference between treatment arms in the HAM-D6 score at Visit Week 8 after controlling for baseline and other covariates. For the ITT population, a restricted maximum likelihood (REML) based linear MMRM approach will be used to test for systematic differences in change between arms over time, after accounting for participant-specific heterogeneity in HAM-D6 scores residual error structure. The MMRM will be parameterized to include random effects for site and repeated measures for post-baseline visits using an unstructured residual covariance structure (3 parameters); in the unlikely event that the unstructured covariance matrix fails to converge, the model will be refit with a first order autoregressive covariance matrix (2 parameters).

Sponsor Name: Woebot Health

Protocol Number: WB001-001

This test will be performed using the final, MMRM model-based t-test with a two-sided significance level of 5%. Estimated least squares means for change from baseline and the observed absolute values (\pm SE) at each visit by treatment group will be plotted over time.

No explicit imputation will be performed; the MMRM model described above will be run on this population, which implicitly imputes missing data under a missing at random (MAR) assumption.

As a sensitivity analysis for the primary analysis using ITT population, MMRM model in the same manner as described above will be conducted in the PP population.

The treatment effectiveness on MIBS, EPDS, PHQ-9, and GAD-7 (difference between arms at Week 8, controlling for baseline) will be evaluated using the same analysis plan proposed for the analysis of the primary endpoint (HAM-D6).

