9.2 SECONDARY ENDPOINTS

The treatment efficacy of MIBS, EPDS, PHQ-9, and GAD-7 (difference between arms at Week 8, controlling for baseline) will be evaluated using the same analysis plan proposed for the analysis of the primary endpoint (HAM-D). In addition, the differences in HAM-D6 scores between baseline and week 8 within each treatment arm will be calculated. Secondary endpoints are not powered to detect a significant difference between treatment groups and no sequential testing will be applied.

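### Four between-arm secondary tests run at two-sided 0.05 with no gate on HAM-D6, no multiplicity control and no label of nominal in the visible protocol

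*Combined protocol and SAP*

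**What the plan says.** Section 8.1 (General Methodology) gives the default: "All statistical tests will be 2-sided and performed at the 0.05 level of significance unless stated otherwise". It treats one class of endpoint separately: "Descriptive analyses and p-values will be presented for exploratory endpoints". The secondary endpoints are not mentioned there, so the default covers them.

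The synopsis lists the between-arm secondary endpoints as "Difference between arms in the following assessments at EOT, controlling for BL and other covariates", followed by EPDS, MIBS, PHQ-9 and GAD-7. Section 9.2 takes the same four measures, each as a Week 8 contrast between arms, and says that they "will be evaluated using the same analysis plan proposed for the analysis of the primary endpoint (HAM-D"). The synopsis, under Statistical Methods, describes the primary test: "This test will be performed using the final, MMRM model-based t-test with a two-sided significance level of 5" per cent.

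Section 9.2 then adds: "Secondary endpoints are not powered to detect a significant difference between treatment groups and no sequential testing will be applied". The other secondary endpoint, change in HAM-D6 within each arm, is only to be computed: "the differences in HAM-D6 scores between baseline and week 8 within each treatment arm will be calculated". It is not one of the four between-arm tests.

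**The concern.** Ruling out sequential testing removes a hierarchy but puts nothing in its place. Section 9.2 states no other alpha, so each of the four comparisons falls back on the 0.05 default. No visible text makes these tests depend on the HAM-D6 result, adjusts them for their number, or calls their p-values descriptive. The remark about power concerns missed effects; it does not limit false positives.

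What is at stake is the reading of the secondary results. The four measures are the secondary efficacy aim. If HAM-D6 misses and one of the four gives p < 0.05, the plan has no rule for what may be said about it. Such a rule is credible only if it is written before unblinding. The primary test and its error rate are not affected.

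**Working it through.** The documents state no family-wise error figure for the secondary endpoints, so there is none to reproduce.

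**Inputs from the documents**
- Four between-arm tests at Week 8: EPDS, MIBS, PHQ-9 and GAD-7 (section 9.2).
- Each two-sided at 0.05 (section 8.1). This allows 0.025 in favour of WB001 and 0.025 in favour of the control.
- No adjustment and no gate (section 9.2).

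**Assumptions**
- All four nulls are true, and the HAM-D6 null as well for the figures conditional on a non-significant primary.
- The test statistics are jointly normal with one common correlation r. The documents give no correlations, so a range is shown.

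**Independent tests**
- At least one p < 0.05 in either direction: 1 − 0.95^4 = 1 − 0.8145 = 0.1855.
- At least one significant result favouring WB001: 1 − 0.975^4 = 1 − 0.9037 = 0.0963.

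**Correlated tests**

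The figures come from simulating five equicorrelated normal statistics (the primary and four secondaries), 4 million trials per value of r, and were confirmed by numerical integration. The last two columns are conditional on a non-significant primary that has the same correlation r with the secondaries.

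| r | Either direction | Favouring WB001 | Either direction, primary not significant | Favouring WB001, primary not significant |
|---|---|---|---|---|
| 0 | 18.5% | 9.6% | 18.5% | 9.6% |
| 0.3 | 17.4% | 8.7% | 16.7% | 8.4% |
| 0.5 | 15.6% | 7.8% | 14.0% | 7.0% |
| 0.7 | 13.0% | 6.5% | 10.4% | 5.2% |
| 0.8 | 11.4% | 5.7% | 8.1% | 4.1% |
| 0.9 | 9.4% | 4.7% | 5.4% | 2.7% |

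A mixed structure, with 0.7 among EPDS, PHQ-9 and GAD-7 and 0.3 between each of these and MIBS, gives 14.9% in either direction and 7.5% favouring WB001.

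**Comparison with a single test.** One two-sided 5% test allows 2.5% for a false benefit. The four together allow 6.5/2.5 = 2.6 to 9.6/2.5 = 3.8 times that for r from 0.7 to 0.

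**With control.** Hochberg across the four tests brings the either-direction figure to 4.7%, 4.4% and 3.8% at r = 0.3, 0.5 and 0.7. Under Hochberg or Holm, if the other three tests have p > 0.05, the remaining one needs p ≤ 0.05/4 = 0.0125.

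**The case against.** The strongest defence is that this is a disclosed and conventional choice. There is one primary endpoint with one 5% test, and its error rate is intact. Section 9.2 says openly that the secondaries are not powered. Unadjusted, supportive secondary analyses are common, and strong control matters only when secondaries carry confirmatory claims. This stands as a reason to keep the point modest, and it is why a purely nominal label is an acceptable remedy. It does not remove the gap: the protocol reserves descriptive treatment for the exploratory endpoints and nowhere says that the secondaries are supportive only.

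Three stronger readings are tempting, and the documents do not support them.

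- A reader might take 13% to 19% as the chance of a false benefit for WB001. The tests are two-sided, so that range includes apparent harm. The false-benefit figure is half as large, about 6.5% to 10%.
- A reader might infer that the sponsor means to claim a secondary effect after a failed primary. No passage says so. Improved mother-infant bonding appears in the benefit/risk section as a possible benefit of taking part, not as an efficacy claim. The protocol leaves such a claim open but does not announce it.
- A reader might conclude that no control exists anywhere. Section 8.1 says the SAP will expand on the protocol, and sections 5.5, 9.3 and 9.9 defer to it. That SAP text is not in the file reviewed. Section 9.7 also refers to a Model 3 in section 9.1 that the visible section 9.1 does not contain. The absence can be asserted only for the visible protocol.

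The size also depends on the correlations. EPDS and PHQ-9 both score depressive symptoms by self-report, so a high correlation for that pair is plausible, and it would pull the figures towards the lower rows of the table.

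**Conclusion.** The point holds for the visible protocol text: four between-arm secondary tests at two-sided 0.05 each, with no gate on HAM-D6, no multiplicity control and no label of nominal. Under four true nulls, the chance of at least one p < 0.05 in either direction is about 13% to 19% for assumed common correlations of 0.7 to 0, falling to about 9% at 0.9. The chance of at least one false benefit for WB001 is about 6.5% to 10% over 0.7 to 0. Given a non-significant primary with the same correlation it is about 5% to 10%. These sizes rest on assumed correlations, and an adjustment in the unseen SAP would answer the point. It is a cheap improvement that should be made; it does not threaten the primary inference.

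**What to change.** Replace the sentence on sequential testing in section 9.2, add the matching exception to the 0.05 default in section 8.1, and carry both into the SAP before unblinding:

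1. No significance claim is made for EPDS, MIBS, PHQ-9 or GAD-7 unless the HAM-D6 primary test is significant at two-sided 0.05. If it is not, report estimates with 95% confidence intervals labelled nominal.
2. If it is significant, choose one of two options now. Either apply Hochberg or Holm across the four tests at a family-wise 0.05 or, in keeping with the decision not to test sequentially, report all secondaries as estimates with 95% confidence intervals labelled nominal. Holm needs no assumption about the correlations.

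If the SAP already contains such a rule, bring sections 8.1 and 9.2 into line with it.

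The cost is wording only; the primary alpha and the planned 210 participants do not change. There are two downsides. A lone secondary result would need p ≤ 0.0125 under Hochberg or Holm, and no secondary significance claim is possible if HAM-D6 misses.

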8.2 ANALYSIS POPULATIONS

For the purposes of analysis, the following analysis sets are defined in [Table 4](#) below.

TABLE 4. SUMMARY OF ANALYSIS SETS

Analysis Set	Description
Enrolled	All participants who signed the ICF
Intention-To-Treat (ITT)	All randomized participants with HAM-D6 measured at baseline. Participants will be included in the ITT population regardless of how often they engage with WB001 or ED001. This analysis set will be the primary set used for analyses/summaries of the primary efficacy endpoint, as well as for all secondary and exploratory efficacy endpoints.
Per-Protocol (PP)	All randomized participants also in the ITT population who complete 8 weeks of treatment and have at least 75% compliance on engaging with the Woebot application at least 1 day per week, and who have HAM-D measured at baseline, Week 4, and Week 8, with no other major protocol deviation that could affect the interpretability of the efficacy outcome. This analysis set will be used for sensitivity analyses.
Safety	All randomized participants who used WB001 or ED001 and who have at least one post-baseline safety assessment (i.e., C-SSRS). This analysis set will be used for summaries of safety data.

*Note: Inclusion criteria at screening will assess for participants engagement in TAU. If participant is confirmed as not having completed TAU by EOT, the data from these patients will be excluded from the primary analysis; however, their data will be retained for the purpose of conducting exploratory analysis.
	

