Study Design: This protocol comprises a randomized, double-blind, controlled trial to assess the efficacy and safety of 8 weeks of treatment with either [WB001+TAU] or [ED001+TAU] in a population of women with mild to moderate PPD. Patients will be referred by an obstetrician, pediatrician, or other healthcare professional, or by other digital and site based recruitment methods and if interested, will complete the pre-screening process. Those confirmed as eligible will be scheduled to attend a screening/baseline onsite visit, at which they will complete an informed consent form and the Principal Investigator (PI), or qualified site staff and Central Independent Rater (CIR) will conduct screening assessments. The PI or sub-investigator will determine participant eligibility. Eligible participants will be randomized to one of the two groups and will receive instructions on downloading and using the smartphone application (app) to which they were randomized. Participants will use the app as instructed and will attend telehealth visits with the CIR who will administer an assessment for the primary endpoint (e.g., HAM-D6) and PI/qualified site staff who will administer key assessments for the safety endpoints at Weeks 4 and 8 by video call (preferred) or telephone. Participants will also complete several questionnaires (electronic patient-reported outcomes [ePROs]) on their own. All assessments will be completed within 3 days prior to or 3 days (± 3) after participants' Week 4 and Week 8 key assessment visit date.

Study Duration: 8 weeks

Target Population: Women with mild to moderate PPD who are ≤ 92 days postpartum

Key Inclusion Criteria:

- Must have primary residence in the United States
- Must be willing to comply with all study procedures and restrictions
- Must be able to understand and willing to provide informed consent
- Must be ≤ 92 days postpartum at the time of screening
- Must be women aged 22-45 years who had onset of a major depressive episode any time during pregnancy or within 4 weeks following delivery according to DSM-5 diagnostic criteria (Segre et al., 2013)
[REDACTED]
- Must own or have regular access to a smartphone (Android or iOS smartphone with a recent, supported operating system), and has reliable Wi-Fi access or sufficient data plan to engage with assigned treatment condition for the duration of the study

Sponsor Name: Woebot Health

Protocol Number: WB001-001

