However, potential risks include the opportunity cost of seeking alternative treatment, device software failure, leading to delayed access, information security breaches, and potentially brief emotional stress that may result from attending key assessment visits, completing survey questions that cover sensitive topics, and discontinued access to the assigned study intervention at the end of study (Week 8).

Several aspects of the study design will mitigate these potential risks of participating in the study:

- [REDACTED]
- adjunct.
- The eligibility criteria will exclude patients with severe psychiatric diagnoses (e.g., psychosis, history of attempted suicide or current suicidal ideation, substance use disorder).
- Concomitant medications and psychotherapy are allowed during the study period per standard of care as prescribed and administered by trained professionals, as long as the medication doses and frequency of psychotherapy are stable for at least 4 weeks before the Baseline visit. The study will capture any changes (e.g., starting or stopping a medication or any change in medication dose or frequency, as well as changes in frequency of psychotherapy).
- [REDACTED]

Sponsor Name: Woebot Health

Protocol Number: WB001-001

- Survey Questionnaires have been thoughtfully selected to minimize the risk of emotional upset due to the topics covered.
- Woebot performing appropriate software verification and validation testing to demonstrate that the device's behavioral therapy has been correctly implemented so that the participant can access it when needed.
- All study data will be gathered on a secure Health Insurance Portability and Accountability Act (HIPAA)-compliant web platform and will be encrypted to minimize the risk of a data breach.
- Participants will be informed that they may leave the study at any time and can receive appropriate referrals for alternative treatment.
- Participants will have contact with the investigator and/or designated clinical rater at each study assessment time point, who will administer validated psychometric assessments to monitor for worsening symptoms and/or the development of suicidal ideation.
- Study withdrawal criteria are designed so that participants who experience worsening of symptoms can withdraw from the study to receive additional treatment, per PI recommendation.

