4. STUDY POPULATION

Eligible participants who are enrolled in the trial will be assigned a unique participant randomization number for study app functionality assignment at baseline. Only participants who meet all the inclusion criteria and none of the exclusion criteria will be eligible to participate in the study. Prospective approval of protocol deviations to recruitment and enrollment criteria, also known as protocol waivers or exemptions, is not permitted.

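### The per-protocol engagement rule names only the Woebot app, although the set is drawn from both arms

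*Combined protocol and SAP*

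**What the plan says.** Table 4 in section 8.2 defines the analysis sets. The PP row starts from randomized participants who are in the ITT set, so from both arms. It asks for completion of 8 weeks of treatment, HAM-D at baseline, Week 4 and Week 8, and no other major deviation that could affect interpretation of efficacy. It also requires that participants "have at least 75% compliance on engaging with the Woebot application at least 1 day per week".

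The neighbouring rows are worded differently. The ITT row includes participants "regardless of how often they engage with WB001 or ED001", and the Safety row begins "All randomized participants who used WB001 or ED001". The synopsis describes the comparator under Control Device: "The educational control application is an educational app named ED001".

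Under Statistical Methods, the synopsis gives the use of the PP set. As a sensitivity analysis of the primary endpoint, the "MMRM model in the same manner as described above will be conducted in the PP population". That is a comparison between arms.

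**The concern.** The PP row is the only row of Table 4 that turns app use into a threshold, and it is also the row that does not name the control app. A participant randomized to ED001 does not, on the face of it, use the Woebot application. The wording therefore leaves three ways to build the set, and they give different sets.

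At stake is the PP sensitivity analysis of the primary endpoint. It would either lose its control arm or, if the rule were applied to WB001 users only, compare women selected for engagement with women who were not. Engagement is measured after randomization and may be related to outcome, so a one-arm filter could bias the comparison in a way that the same filter in both arms is less prone to do. Membership should have a single reading before anyone sees allocation. Section 8.1 has the analysts work separately until quality control, so the definition should not depend on each of them inferring the same meaning.

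**Working it through.** No figure in the plan is disputed, so there is none to reproduce. The check is textual, with simple arithmetic.

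**Inputs**
- Planned sample: 210 (synopsis), allocated 1:1 (synopsis, Study Conditions).
- Treatment period: 8 weeks.
- PP threshold: 75% compliance with use on at least 1 day per week (Table 4).

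**Arithmetic**
- Per arm: 210 / 2 = 105.
- Weeks required: 0.75 × 8 = 6.
- Least use that satisfies the rule: 6 weeks × 1 day = 6 days out of 8 × 7 = 56, or 6 / 56 = 10.7% of days. The filter is light.

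**What 'Woebot' means in the document**
- *Product or agent.* Section 1.4 describes users forming a working alliance with Woebot, and section 4.2 excludes women who have used it before. The Client Satisfaction Questionnaire entry in section 5.2 treats WB001 and ED001 as two applications.
- *Sponsor.* The Benefit/Risk Assessment has "Woebot performing appropriate software verification and validation testing", which is the company. On this sense, the phrase in Table 4 could loosely mean any app the sponsor supplies.
- *Neutral wording used elsewhere.* The smartphone criterion (synopsis and section 4.1, item 7) asks for the means "to engage with assigned treatment condition for the duration of the study". Section 4 speaks of a "unique participant randomization number for study app functionality assignment at baseline".

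The document therefore has arm-neutral wording available, but the PP row does not use it. No visible passage says that the term in Table 4 covers ED001.

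**The three readings**

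The documents give no usage rate. Purely for illustration, assume that 50% to 90% of women meet the threshold, at the same rate in both arms, and ignore the other PP conditions. Then 105 × 0.50 to 105 × 0.90 is about 52 to 94 women.

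| Reading | WB001 | ED001 | Consequence |
|---|---|---|---|
| Literal: everyone must use Woebot | about 52–94 | 0 | No between-arm comparison |
| Rule applied to WB001 only | about 52–94 | up to 105 | Engagement filter in one arm |
| Rule applied to the assigned app | about 52–94 | about 52–94 | Same filter in both arms |

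The zero in the first row follows from the wording alone. The other counts rest on the assumed rates. No bias can be calculated for the second reading, because the documents give neither usage rates nor outcomes by usage.

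**The case against.** The strongest reply is that the intended meaning is clear from context. A two-arm model cannot be run without controls, so the literal reading defeats itself. The row contains no words exempting controls from the engagement rule, so applying it to WB001 only would be a misapplication. Blinding points the same way: section 8.1 keeps analysis personnel blinded until database lock and identification of protocol deviations, and Table 2 lists the independent statistician and programmers as blinded. They could not apply an arm-specific rule without allocation, which suggests that an arm-neutral rule was meant.

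There is more on that side. Controls must still meet every other PP condition, and section 4.6 (item 4) provides for discontinuing noncompliant participants in either arm, so controls would not go unfiltered. Section 8.1 leaves detail to the SAP, and parts of section 3 and Appendix 2 are redacted; a definition may exist in either place. The multiple-imputation analyses in section 9.8 also mean that the PP model is not the only sensitivity analysis.

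Most of this stands. It supports the assigned app as the likely intent and keeps the point minor. It does not remove the mismatch: the inconsistency lies between unredacted rows of one table, and the benign reading has to be inferred. The blinding argument is also a reason to write the arm-neutral rule down.

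**Conclusion.** The concern holds, in a narrow form and as a minor point. The PP engagement criterion names one app where the set, the adjacent rows and the planned analysis all involve two. Followed exactly, it admits 0 of about 105 ED001 participants. Applied to WB001 only, it would filter one arm on engagement, with a bias whose size and direction cannot be derived from the documents; because 6 days of use in 56 can satisfy the rule, it might remove few women. Applied to the assigned app in both arms, there is no one-arm effect.

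Confidence is high on the wording mismatch itself. Whether it would affect the trial depends on two things that cannot be seen: whether the SAP or redacted text defines the term, and how the analysts would read it. The ITT primary analysis, sample size, power and alpha are unaffected.

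**What to change.** Before unblinding, replace the app name in the PP row of Table 4 with *the assigned study application (WB001 or ED001)*. Add one sentence saying that the rule means at least 1 day of use in at least 6 of the 8 weeks and applies identically in both arms. Use the same wording in the SAP; if the SAP already defines the term this way, only Table 4 needs aligning.

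The cost is one phrase and one sentence. Table 4 already refers to use of both apps in its ITT and Safety rows, which implies that use is recorded in both arms, so little or no new data collection should be needed. No visible text describes usage logging, so the sponsor should confirm this. Selection on post-randomization engagement will remain in both arms, as in any PP analysis.
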